This randomized, controlled, double-blind clinical trial was approved by the Ethics Committee of Izmir Katip Celebi University (Approval No: 14/100). Informed consent was obtained from parents, and the study adhered to CONSORT guidelines. A total of 200 healthy children (ASA I), aged 6–12 years, each with two fully erupted permanent mandibular first molars (400 teeth), were enrolled. Using a split-mouth design, one molar received a high-fluoride glass ionomer-based sealant (Fuji Triage, GC Corp., Tokyo, Japan; control), while the contralateral molar was treated with either a CPP-ACP-containing sealant (Fuji VII EP, GC Corp.) or a nano-fluorohydroxyapatite-based sealant (GCP Glass Seal, GCP Dental, The Netherlands). Sample size was calculated using G*Power 3.1.9.7, assuming an effect size of 0.40, $\alpha = 0.05$, and power = 0.80, yielding a minimum of 88 teeth per group. Considering a 15–20% potential loss, the final sample included 400 teeth. Inclusion criteria comprised children demonstrating cooperative behavior (Frankl scores 3–4) and having deep fissures without caries (ICDAS II; DIAGNOdent ≤ 15). Exclusion criteria included systemic disease (ASA $\geq II$), uncooperative behavior, enamel defects, or inability to attend follow-ups. Bitewing radiographs excluded proximal caries. Two calibrated examiners (Cohen's $k \geq 0.8$) conducted the study. Screening of 295 children included health history, caries risk assessment (Cariogram software, Malmö University), and inclusion of those with moderate caries risk. Randomization was two-phased: material pairing (Fuji Triage–GCP Glass Seal / Fuji Triage–Fuji VII EP) was determined using an online randomizer, while tooth allocation (right/left) was assigned by coin toss. Blinding was maintained for participants and evaluators. Before sealant application, baseline data (age, sex, oral hygiene, ICDAS II, and DIAGNOdent scores) were recorded. Teeth were cleaned and isolated; materials were applied per manufacturers' instructions. For Fuji materials, cavity conditioner was used for 10 s, followed by sealant placement, coating, and 20 s LED curing. GCP Glass Seal involved EDTA cleaning, 60 s light-curing, and surface coating with GCP Gloss. All restorations were inspected for marginal adaptation and polymerization, and occlusion was adjusted. Oral hygiene instructions were provided. Follow-up evaluations were conducted at 3, 6, 12, 18, and 24 months by a blinded examiner. Retention, marginal integrity, discoloration, and secondary caries were assessed using modified USPHS criteria. Retention was graded (1 = complete, 2 = partial, 3 = total loss); further caries evaluation (ICDAS II and DIAGNOdent) was performed for scores 2–3.

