
STATİSTİCAL ANALYSIS PLAN

Data were analyzed using IBM SPSS v21. Descriptive statistics were expressed as mean \pm SD or percentage. Normality was assessed with the Kolmogorov–Smirnov test. Non-parametric tests (Friedman, Kruskal–Wallis with Bonferroni correction) were used where appropriate. Categorical data were analyzed using Fisher-FreemanHalton, Pearson chi-square, or Fisher’s exact tests. Kaplan–Meier curves and log-rank tests compared material survival. Statistical significance was set at $p < 0.05$.

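### The plan compares materials only by significance tests, with no difference, confidence interval or margin, so a non-significant result against the active control cannot show similar performance

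*Combined protocol and SAP*

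**What the plan says.** The statistical analysis plan is a single paragraph. It provides three kinds of output: summaries by group (means with SDs, or percentages), Kaplan–Meier curves, and hypothesis tests. The tests are Friedman and Kruskal–Wallis with a Bonferroni correction; Pearson chi-square, Fisher's exact and its Freeman–Halton extension for categorical data; and the log-rank test for survival. The criterion is "Statistical significance was set at $p < 0.05".

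The protocol text sets the context:

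- Comparator: "one molar received a high-fluoride glass ionomer-based sealant (Fuji Triage, GC Corp., Tokyo, Japan; control". It is an active material.
- Design: "Using a split-mouth design", with each test sealant in the contralateral molar of the same child.
- Outcomes: "Retention, marginal integrity, discoloration, and secondary caries were assessed using modified USPHS criteria". None is named as primary.
- Visits: "Follow-up evaluations were conducted at 3, 6, 12, 18, and 24 months by a blinded examiner".
- Size: "assuming an effect size of 0.40, $\alpha = 0.05$, and power = 0.80, yielding a minimum of 88 teeth per group", then "Considering a 15–20% potential loss, the final sample included 400 teeth".

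Neither the protocol text nor the SAP states a superiority, non-inferiority or equivalence hypothesis, a margin, an expected retention or caries rate, or any between-material estimate with its precision.

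**The concern.** The useful question is by how much each test sealant is better or worse than Fuji Triage. A p-value does not answer it. When the control is also a sealant, a modest true difference and a non-significant test are both plausible. The plan then offers nothing to tell materials that perform alike from data that could not tell. A material with a material loss of retention could sit in the same "not significant" category as one that matches the control.

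The split-mouth design makes the omission harder to repair afterwards. The precision of a within-child difference depends on how many children had different results on the two sides. Percentages by material and separate survival curves do not carry that count.

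**Working it through.** **1. The plan's own figure.** The only sizing figure is 88 teeth per group, from an effect size of 0.40, alpha 0.05 and power 0.80. It could not be reproduced. A two-sided independent t-test at d = 0.40 needs 100 per group, and a two-sided paired t-test needs 52 pairs. The test and the type of effect size are not stated. That is a separate matter and nothing below depends on it. What matters here is that 0.40 is not expressed as a difference in retention or caries, so it says nothing about the precision of the comparison.

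**2. Inputs.**

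- 200 children and 15–20% loss: from the protocol text.
- 100 children per pairing: assumed, because the split is not given.
- Pairs left at 20% loss: 100 × 0.80 = 80.
- Discordance in complete retention of 20–40% of pairs: assumed, because the documents give no figure.
- Caries rates of 2–30% per control tooth: assumed, for the same reason.

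**3. Precision for retention.** The approximate 95% half-width for a paired difference is 1.96 × √(discordance / n).

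| Discordance | Calculation | Half-width |
|---|---|---|
| 20% | 1.96 × √(0.20/80) | 9.8 points |
| 30% | 1.96 × √(0.30/80) | 12.0 points |
| 40% | 1.96 × √(0.40/80) | 13.9 points |

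**4. One non-significant result.** At 30% discordance there are 0.30 × 80 = 24 discordant pairs. A 10-point deficit is a net 8 pairs, so the split is 16 v 8.

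- Exact McNemar: 2 × P(X ≤ 8) for Binomial(24, 0.5) = 0.15.
- Standard error of the difference: √(24 − 8²/80) / 80 = 4.82/80 = 6.0 points. The 95% interval for the deficit is 10 ± 11.8, that is −1.8 to 21.8 points.

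McNemar's test is not on the SAP's list, but the listed unpaired tests agree. With a 16 v 8 split, the uncorrected Pearson statistic is largest when the failures are 16/80 and 8/80: 0.10² / (0.15 × 0.85 × 2/80) = 3.14, p = 0.077. The planned output is "not significant" while the data allow a deficit of about 22 points.

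**5. Group percentages do not give the paired interval.** The same 10-point difference in 80 pairs arises from discordant splits of 12 v 4 (20%), 16 v 8 (30%) or 20 v 12 (40%). Using the half-widths above, the deficit could reach 10 + 9.8 = 19.8, 10 + 12.0 = 22.0 or 10 + 13.9 = 23.9 points. The percentages by material can be identical in all three.

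**6. Caries.** Fisher's exact test at 80 v 80 gives p = 0.059 for 5 v 0 carious teeth and p = 0.028 for 6 v 0. So if one side has no caries, six cases on the other are needed. The chance of a non-significant result when the test sealant truly halves caries (exact calculation, sides treated as independent) is:

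| Assumed control rate | Rate if halved | Non-significant, 80 v 80 |
|---|---|---|
| 2% | 1% | 99.7% |
| 5% | 2.5% | 96% |
| 10% | 5% | 86% |
| 20% | 10% | 65% |
| 30% | 15% | 44% |

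An exact McNemar test with 80–100 pairs and a within-child correlation of 0 to 0.5 is non-significant in 70–86% of trials at 10% and 27–66% at 20%. The result therefore depends strongly on the rate, which the documents do not supply.

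**The case against.** Four points can be made for the plan.

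*The estimates are nearly there.* Percentages and survival curves by material are planned, so a reader can subtract and, with denominators, form a rough unpaired interval. This is true and it narrows the gap. It does not close it, because the paired interval cannot be recovered (step 5 of the working).

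*No one has said that non-significance will mean equality.* This stands. A reader might infer that the trial intends to conclude equal performance from p ≥ 0.05, but neither document says so and no equivalence aim is stated. The supportable point is that the plan gives no means of preventing or answering that reading.

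*Caries may not be rare.* A reader might infer that the caries comparison is almost bound to be non-significant, since teeth enter caries-free and both sides are sealed. The documents do not support that as a general statement. They give no caries rate, and the children are at moderate caries risk with deep fissures and 24 months of follow-up. Under a true halving the inference is well supported up to about 5%, mostly supported at 10%, and not supported at 20–30%.

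*The text is in the past tense.* A margin set now may come after unblinding. This also stands, and it limits what the fix can offer.

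**Conclusion.** The point holds in a limited form. The plan contains tests and summaries by group, but no between-material estimate, interval or margin. A non-significant comparison with Fuji Triage therefore cannot separate similar performance from insufficient information.

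This conclusion comes from the text and needs no assumed rate. Its size does: a half-width of about 10–14 points for retention rests on an equal split of children, 20% loss and 20–40% discordance. For caries, the chance of missing a true halving runs from 99.7% at a 2% control rate to 44% at 30%, and must be quoted as that range.

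The change should be made, but the listed tests can still be reported. What is at risk is the interpretation of a null result.

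**What to change.** For each test sealant against Fuji Triage:

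- Report the 24-month difference in complete retention with a paired 95% score interval, and show the discordant-pair counts.
- Add to the log-rank test a survival contrast, either a hazard ratio or a difference in Kaplan–Meier survival, with an interval that respects the pairing within child.
- Report caries as counts and as a paired difference with an exact 95% interval, alongside any test. The test need not be dropped.
- State that p ≥ 0.05 alone supports no claim of similar performance. Such a claim should be made only against a margin fixed before unblinding. If unblinding has already occurred, report the intervals and make no similarity claim.

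The design provides outcomes for both teeth of each child at every visit, so no new data are needed. The cost is SAP wording and a few lines of output. The downside is that some non-significant results will have to be reported as inconclusive.
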